### **10.5.3 Safety Analysis Plan**

Safety evaluations will be based on the incidence, severity, and type of AEs, SAEs, clinically significant physical and pelvic examination findings as detailed in [Section 9](#). In addition, the incidence of culture confirmed secondary VVC will be evaluated. Safety variables will be tabulated and presented for all participants in the safety population, grouped by type of infection and treatment.

AEs and SAEs will be coded by MedDRA® for preferred term and system organ class. The rate and exact 95% confidence intervals (CIs) of AEs in aggregate, as well as by MedDRA® categories, will be computed. The number of SAEs is likely to be small in this study and will be reported by a detailed listing showing the type, MedDRA® coding, relevant dates (IP administration dates and AE onset and resolution dates), severity, relatedness, and outcome for each event.

The occurrence of culture confirmed secondary VVC following initiation of study treatment and through the final study visit will be summarized in aggregate and by treatment group.

### **10.5.4 Efficacy Analysis Plan**

#### **10.5.4.1 Primary Efficacy Analysis**

The primary efficacy analysis estimates the clinical efficacy rate of TOL-463. At each follow-up visit, the following Amsel criteria will be assessed:

- a. Positive KOH whiff test
- b. Homogeneous discharge characteristic of BV
- c. Clue cells  $\geq 20\%$  of vaginal squamous epithelial cells
- d. Vaginal pH  $> 4.5$

For the primary analysis, a participant is deemed to experience a recurrence of BV at a follow-up visit if  $>2$  of the above criteria are met. A participant has clinical suppression of BV if she meets two or fewer of the criteria at each observed follow-up visit through V4.

The proportion of participants with recurrent BV up to and including V4 will be summarized overall and by treatment group along with two-sided 95% Wilson CIs. The primary analysis will be performed in the mITT analysis population. Secondary analyses of the primary outcome measure will be performed in the PP analysis population. Recurrence status of participants who

---

are withdrawn or drop out early before an observed recurrence will be imputed; multiple imputation methods may be explored, and details will be provided in the SAP document.

In addition, the rate of recurrence, which considers the amount of observed follow-up time for each participant, will be estimated within each treatment group along with corresponding 95% CIs. Any additional sensitivity and/or corroborative analyses to be performed will be described in the separate SAP document.

#### **10.5.4.2 Secondary Efficacy Analyses**

The secondary efficacy analyses are briefly described below. Secondary efficacy analyses will be performed in the mITT and PP analysis populations, where appropriate. Details of these analyses and any sensitivity analyses will be specified in the separate SAP document.

For the analysis of Secondary Objective 1, the median time to BV recurrence will be estimated by treatment group using Kaplan-Meier estimates. For participants who experience BV recurrence by V4, the time of BV recurrence will be defined as the midpoint between the earliest time point of a positive BV diagnosis (post-baseline) and the previous observed time-point. For participants without BV recurrence at or before V4, the BV recurrence endpoint will be coded as censored, with time to recurrence defined as the elapsed time from the first dose of IP, to the earliest of: V4 time-point, the last observed time-point prior to loss to follow-up, or the time-point at which the participant became ineligible for the particular analysis population.

For the analysis of Secondary Objective 2, the proportion of participants experiencing vaginal symptoms as assessed by the participant via the daily memory aid will be estimated overall, by symptom category, and by treatment group.

For the analysis of Secondary Objective 3, responses to the satisfaction questionnaire will be summarized overall and by treatment group. Categorical responses will be summarized using contingency tables and/or odds ratios, while continuous responses will be summarized using measures of central tendency such as the mean or median, and measures of dispersion such as the standard deviation or interquartile range.

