### 10.2 Sample Size Considerations

As detailed in [Section 10.5](#), efficacy analyses will be performed in an evaluable subset of the enrolled population; this subset was used to derive the study's sample size. Assuming a 40% BV recurrence rate among women receiving placebo and a 50% reduction in recurrence among women treated with TOL-463 (i.e. 20% recurrence rate among TOL-463 recipients) and a 1:1 allocation ratio between treatment arms, a sample size of 200 evaluable participants will provide at least 85% power using the Chi-Square Test. Assuming 80% of enrolled participants will be evaluable for the primary analysis, the enrollment target is set to 250 to achieve 200 evaluable participants.

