8.2. Secondary Efficacy Analyses

Secondary efficacy analyses will be performed in the mITT as the primary population. All the analyses will be repeated in the PP analysis populations as corroborative and sensitivity analyses.

The analysis of Secondary Objective 1, time to BV recurrence will take into account the observed follow-up time for each participant (time-to-event analysis). For this analysis, the outcome will be the time to RBV diagnosis in days from the enrollment visit (day 1). For the participants whose RBV was diagnosed at a scheduled or unscheduled visit, their time of BV recurrence will be defined as the midpoint between the earliest time point of a positive BV diagnosis (post-baseline) and the previous observed time-point. For participants without BV recurrence at or before V4, the BV recurrence endpoint will be coded as censored, with time to recurrence defined as the elapsed time from the first dose of IP, to the earliest of: V4 time-point, the last observed time-point prior to loss to follow-up, or the time-point at which the participant became ineligible for the particular analysis population. Participants with missing time to BV recurrence will be further excluded from analyses in mITT and PP populations, including subjects who had BV recurrence diagnosed off study or subjects who were unknown whether they used any study products. The individual time to BV recurrence defined for secondary objective 1 for mITT and PP populations are also provided in [Listing 7](#).

The null hypothesis for the comparison is that there is no difference in the time to BV recurrence throughout the study between treatment arms, with a two-sided alternative that considers the possibility of a difference in either direction. Kaplan-Meier (KM) curves and associated 95% confidence bands (by treatment groups) will be presented to visually assess the treatment group-specific time-to-recurrence pattern over time. The median time to BV recurrence cannot be calculated because the assumed BV recurrence in the two treatment groups are 20% and 40%. Appropriate quartiles of the time to recurrence will be presented by each treatment group and overall. The KM curves will be presented in [Figure 3](#) for mITT population and in [Figure 4](#) for PP population. The estimate of survival time at which 25% of the subjects have recurrent BV, i.e., 25th percentile of the time to recurrence, by each treatment group and overall will be described in the footnote of the figures.

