The pseudocode to fit the above analyses is below:

```
proc lifetest method=KM plots=survival(cb=hw test=atrisk) data=dataset outs=surv;
  strata treatment / test=logrank;
  Time time*censor(censored_value);
run;
```

For the Secondary Objective 2, the proportion of participants experiencing vaginal symptoms will be estimated overall, by symptom category, and by treatment group at each visit. See [Table 15](#) for mITT population and [Table 16](#) for PP population. A subject listing of BV symptoms will be presented ([Listing 8](#))

For the Secondary Objective 3, responses to the satisfaction questionnaire will be summarized overall and by treatment group. See [Table 17](#) for mITT population and [Table 18](#) for PP population. Individual subject listings will be presented for all responses to satisfaction questionnaire ([Listing 9](#)).

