APPENDIX 2. FIGURE MOCK-UPS

LIST OF FIGURES

Figure 1: Schematic of Study Design.....	7
Figure 2: CONSORT Flow Diagram	86
Figure 3: Time to Bacterial Vaginosis Recurrence - mITT population	87
Figure 4: Time to Bacterial Vaginosis Recurrence - PP population	87
Figure 5: Number and Severity of Unsolicited Adverse Events by MedDRA System Organ Class - Safety Population.....	88
Figure 6: Number of Unsolicited Adverse Events by MedDRA System Organ Class and Relationship - Safety Population	89

Figure 2: CONSORT Flow Diagram

[figure not shown]
[figure not shown]

Figure 3: Time to Bacterial Vaginosis Recurrence - mITT population

[Implementation notes: 3 curves are for overall and each treatment group. X-axis label: Time (Days) to Bacterial Vaginosis Recurrence, x-axis label: Proportion of Survival.

[figure not shown]
Display, number of subjects at risk table with ticks at day 0, 15, 30, 45, 60, 75, 90 on x-axis, and 95% HW confidence bands of the curves in the plot. Legend names: Treatment arm, All, TOL-463 Vaginal Insert, Placebo. Obtain the estimates in the footnote from the SAS proc lifetest Quartile Estimates output table.]

Notes: The estimate of survival time at which 25% of the overall subjects are expected to have recurrent BV (Proportion of survival equals to 0.75 at y-axis) is **X** days (95% CI: **X - X**), and correspondingly, **X** days (95% CI: **X - X**) for the TOL-463 group and **X** days (95% CI: **X - X**) for the Placebo group.

[figure not shown]
Figure with similar format:

Figure 4: Time to Bacterial Vaginosis Recurrence - PP population

Figure 5: Number and Severity of Unsolicited Adverse Events by MedDRA System Organ Class - Safety Population

Figures will have 3 panels: TOL-463 Vaginal Insert, Placebo, All Subjects

Show footnote if the following scenario exist: Notes: Subjects are excluded from Safety Population if it is unknown whether they received at least one dose, but the adverse events of such subjects are included in the AE listings

Figure 6: Number of Unsolicited Adverse Events by MedDRA System Organ Class and Relationship - Safety Population

Figures will have 3 panels: TOL-463 Vaginal Insert, Placebo, All Subjects

Show footnote if the following scenario exist: Notes: Subjects are excluded from Safety Population if it is unknown whether they received at least one dose, but the adverse events of such subjects are included in the AE listings

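### Recurrence times are set at visit midpoints and analysed as exact, so the placebo and pooled 25th percentiles largely follow the visit calendar and their 95% CIs have unreliable coverage

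*Protocol*

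**What the plan says.** BV status by Amsel criteria is assessed at V2 (Days 29-35), V3 (Days 57-63) and V4 (Days 85-91), and at unscheduled visits when symptoms arise (Protocol 5, 6.3 and 6.4).

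For Secondary Objective 1, Protocol 10.5.4.2 states that "the time of BV recurrence will be defined as the midpoint between the earliest time point of a positive BV diagnosis (post-baseline") and the observation before it, and plans a Kaplan-Meier median by arm. SAP 8.2 keeps the time as "defined as the midpoint between the earliest time point of a positive BV diagnosis (post-baseline) and the previous observed time-point", and applies this to scheduled and unscheduled visits alike. The code is a standard right-censored analysis: "proc lifetest method=KM plots=survival(cb=hw test=atrisk) data=dataset outs=surv", with a log-rank test.

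The SAP drops the median as not calculable at the assumed recurrence rates and uses the 25th percentile instead. The Figure 3 note in SAP Appendix 2 reads "The estimate of survival time at which 25% of the overall subjects are expected to have recurrent BV" and leaves space for a number of days and a 95% CI, overall and for each arm, taken from the PROC LIFETEST quartile table. Figure 4 repeats this for the per-protocol population. Neither document plans an interval-censored analysis, a sensitivity analysis for event timing, or a caveat on this interval.

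**The concern.** A recurrence first seen at a visit is known only to have begun after the previous negative visit, a gap of about four weeks. The midpoint rule replaces that gap with one day, and the Kaplan-Meier then treats the day as observed. This has two consequences. The printed percentile can take only the values that the visit calendar allows, wherever the true value lies. The confidence limits are event times too, so they are drawn from the same few values and carry no uncertainty about when within the gap the recurrence occurred.

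The 25th percentile is the only numerical time summary planned for Secondary Objective 1. As printed, it would look accurate to the day, with a 95% interval that need not cover at 95%.

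**Working it through.** **Inputs.** Protocol 10.2 gives "Assuming a 40% BV recurrence rate among women receiving placebo", "20% recurrence rate among TOL-463 recipients", a "1:1 allocation ratio between treatment arms", and "a sample size of 200 evaluable participants will provide at least 85% power using the Chi-Square Test". That is 100 per arm, with pooled recurrence (40% + 20%)/2 = 30%.

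**The plan's own figure.** With p = 0.40 and 0.20, n = 100 per arm and two-sided 5%:
power = Φ[(0.20·√100 − 1.96·√(2·0.30·0.70)) / √(0.24 + 0.16)] = Φ[(2.000 − 1.270)/0.632] = Φ(1.154) = 0.876. This meets the stated 85%. Enrolment of 200/0.80 = 250 also agrees. The documents give no precision or coverage figure for the percentile.

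**Where events can fall** (elapsed days from Day 1, in-window scheduled visits, none missed; add 1 for study day):
- found at V2: (0 + 28 to 34)/2 = 14-17
- found at V3: (28 to 34 + 56 to 62)/2 = 42-48
- found at V4: (56 to 62 + 84 to 90)/2 = 70-76

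**Where the true 25th percentile lies.** With constant hazard and recurrence p by time T, t25 = T·ln(4/3)/(−ln(1 − p)).
- Placebo: 84 × 0.2877/0.5108 = 47.3 days (49.0 if 40% is reached at day 87).
- TOL-463: 84 × 0.2877/0.2231 = 108 days, beyond V4.
- Placebo with recurrences spread evenly over time: 84 × 0.25/0.40 = 52.5 days.

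**Simulated coverage of the nominal 95% CI** (1,000 to 4,000 trials per scenario; 100 per arm; visits uniform over their windows unless stated; log-log interval, assumed because the SAP code gives no option):

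| Curve and assumption | True value (days) | Coverage |
|---|---|---|
| Placebo 40%, constant hazard | 47-49 | 80-82% (84.5% with fixed visits) |
| Same, exact event times | same | 94-96% |
| Same, unscheduled visits added | same | 80-84% |
| Same, linear interval | same | 85-88% |
| Placebo 40%, even onset | 52.5 | 87% |
| Placebo 40%, Weibull shape 0.7 | about 38 | 87-94% |
| Placebo 40%, Weibull shape 1.5 | 57-59 | 94-96% |
| Placebo 35%, constant hazard | 58 | 94-95% |
| Placebo 45%, constant hazard | 42 | 74% |
| Pooled, constant hazard | 70 | 82-89% (90-96% with unscheduled visits; 95-96% exact) |
| Pooled, shape 0.7 | 63.5 | 95% |
| Pooled, shape 1.5 | 75 | 70% |

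The Monte Carlo standard error at 82% is √(0.82·0.18/1000) = 1.2 points at most, so the gap to 95% is not noise.

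**Why coverage swings.** In the constant-hazard placebo case with true value 49.0, the upper limit sits below the truth, in the 42-48 band, in 17.8% of trials. The lower limit is too high in 0.3%. So 100 − 17.8 − 0.3 = 81.9%, the simulated 82%. At 45% recurrence the truth (41.9) lies just below the same band, and the lower limit misses it in 25.9% of trials. Coverage depends on where the truth happens to lie relative to the bands.

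**The point estimate.** With constant hazard the placebo estimate falls at 42-48 days in 71-83% of trials and at 70-76 in nearly all the rest. With Weibull shape 1.5 (true value 57 days, coverage 94%) it fell at 42-48 in 56% and at 70-76 in 44%. The nearest attainable value, 48, is 9 days from the truth. Nominal coverage does not rescue the estimate.

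**TOL-463 arm.** The percentile is not reached in about 88% of trials. Coverage is 81-85%, but only 88% even with exact times, so the end of follow-up is the main cause there.

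**The case against.** The midpoint rule is prespecified and disclosed, and Listing 7 prints the individual times. The quantity is a descriptive footnote to a Phase II secondary analysis. The primary comparison of recurrence by V4, with Wilson and Newcombe intervals, does not use event times. The log-rank test is little affected while both arms share one visit schedule. All of this stands, and it limits the weight of the point.

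Some stronger readings are tempting and are not supported:

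- A reader might infer that the interval is too narrow in general, or that 80-85% is its coverage under the planning assumptions. The documents assume 40% and 20% but no hazard shape, and other plausible shapes and rates give close to 95%. The supportable word is unreliable.
- A reader might infer that the curve cannot step outside the three bands. It can. A negative V2 on Day 29 and a positive unscheduled visit on Day 45 give Day 37; a missed V2 and a positive V3 on Day 57 give Day 29. SAP Table 5 anticipates missed and out-of-window visits. When 30% of recurrences prompted an unscheduled visit, about 10% of simulated events fell between the bands. That blurs the pattern and helps the pooled curve, but leaves placebo coverage at 80-84%.
- A reader might infer that Protocol 10.5.4.2 plans this interval. It sets the midpoint rule but plans a median without a CI; the percentile and its CI come from the SAP.

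SAP 5 also says the study closed early, so 100 per arm is not assured. With 50 in the placebo arm, constant-hazard coverage is 86-88%, better but still short.

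**Conclusion.** The point holds for the placebo and pooled percentiles in the Figure 3 and 4 footnotes. That the estimate largely follows the visit calendar comes directly from the visit schedule and the midpoint rule. The coverage result rests on simulation: about 80-85% for placebo at 40% recurrence, 100 participants and constant hazard, against about 95% with exact times, and roughly 70-96% over the other shapes and rates tried. These figures assume a log-log interval and visits within their windows; the actual value will depend on the final sample size and the true timing of recurrences. The point does not extend to the TOL-463 percentile, which is usually not reached, or to the primary test, and it hardly touches the log-rank test. It is a misleading secondary estimate that can be corrected cheaply, not a threat to the trial's main conclusion.

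**What to change.** In SAP 8.2 and the Figure 3 and 4 footnotes, do one or both of the following:

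1. Replace the percentile in days and its CI with cumulative recurrence and 95% CI at V2, V3 and V4, by arm and overall. This is what the visits measure.
2. Record each recurrence as the interval (last Amsel-negative visit, first Amsel-positive visit], right-censor the others at the last Amsel-negative visit, and estimate the curves with an interval-censored method such as PROC ICLIFETEST, available in the SAS 9.4 already specified in SAP 14. Give any percentile as a between-visit interval.

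Keep the midpoint Kaplan-Meier as a sensitivity analysis.

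An interval-censored Weibull fit to simulated placebo data covered 93.8%, 93.4% and 94.0% for shapes 1.0, 0.7 and 1.5, with median estimates of 49.1, 38.4 and 60.0 days against true values of 49.0, 38.3 and 59.3. Coverage of the nonparametric interval-censored estimate was not simulated. An interval built from whole visit gaps covered at least 99%, so it is conservative rather than calibrated.

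The cost is SAP wording and a little more programming, with no new data: Listing 6 already carries Amsel status and study day by visit. The downside is a percentile that looks less precise.

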#### **10.5.4.3 Exploratory and Other Efficacy Analyses**

Descriptions of the analyses to assess the exploratory objective as well as other analyses that will support the primary and secondary efficacy analyses will be provided in the separate SAP document.

---

Examples of additional analyses that will support the primary and secondary efficacy analyses will include, but not limited to, summaries of Nugent scores by visit and treatment group, and explorations of recurrences by demographic and other baseline characteristics.

---

## **11 SOURCE DOCUMENTS AND ACCESS TO SOURCE DATA/DOCUMENTS**

Each participating site will maintain appropriate medical and research records for this trial, in compliance with ICH E6, Section 4.9 and regulatory and institutional requirements for the protection of confidentiality of participants. Each participating site will permit authorized representatives of the DMID, its designees, and appropriate regulatory agencies to examine (and when required by applicable law, to copy) clinical study records for the purposes of quality assurance (QA) reviews, audits, monitoring, and evaluation of the study safety and progress. These representatives will be permitted access to all source data and source documents, which include, but are not limited to, hospital records, clinical and office charts, laboratory notes, memoranda, participants' evaluation checklists, pharmacy dispensing records, recorded data from automated instruments, copies or transcriptions certified after verification as being accurate and complete, microfiches, photographic negatives, microfilm or magnetic media, x-rays, and participant files and records kept at the pharmacy, at the laboratories, and medico-technical departments involved in the clinical trial. Source data are all information, original records of clinical findings, observations, or other activities in a clinical trial necessary for the reconstruction and evaluation of the trial. DCF's will be provided by the SDCC.

---

## **12        QUALITY CONTROL AND QUALITY ASSURANCE**

Following a written DMID-accepted site quality management plan, each participating site is responsible for conducting routine QA and quality control (QC) activities to internally monitor study progress and protocol compliance. The site PI will provide direct access to all study-related sites, source data/DCFs, and reports for the purpose of monitoring and auditing by the sponsor, and inspection by local and regulatory authorities. The site PI will ensure all study personnel are appropriately trained and applicable documentations are maintained on site.

The SDCC will implement QC procedures beginning with the data entry system and generate data QC checks that will be run on the database. Any missing data or data anomalies will be communicated to the participating site(s) for clarification and resolution.

---

## 13 DATA HANDLING AND RECORD KEEPING

### 13.1 Data Management Responsibilities

The site PI is responsible for ensuring the accuracy, completeness, legibility, and timeliness of the data reported.

DCFs will be derived from the eCRFs and provided by the SDCC to record and maintain data for each participant screened and enrolled in the study. All DCFs should be completed in a neat, legible manner to ensure accurate interpretation of data. Black or blue ink is required to ensure clarity of reproduced copies. When making a change or correction, cross out the original entry with a single line and initial and date the change. Do not erase, overwrite, or use correction fluid or tap on the original.

Data reported in the eCRF derived from the source DCFs should be consistent or the discrepancies should be explained.

The sponsor and/or its designee will provide guidance to the site PIs and other study personnel on making corrections to the DCFs and eCRF.

